6.0 STRATIFICATION FACTORS

Patients will be randomized between Arm 1 (afatinib and cetuximab) and Arm 2 (afatinib) using a dynamic balancing algorithm. (24)

Stratification is based on performance status (0-1 vs 2) and EGFR mutation type (exon 19 deletion versus L858R mutation).

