11.0 STATISTICAL CONSIDERATIONS

11.1 Sample Size with Power Justification

The primary objective of the Phase III study is to compare overall survival (OS) in *EGFR* mutation positive, previously untreated, advanced NSCLC patients randomized to afatinib plus cetuximab versus afatinib alone. The primary objective of the Phase II interim analysis is to evaluate if there is sufficient evidence to continue to the Phase III component by comparing progression-free survival (PFS) between patients randomized to afatinib alone versus afatinib in combination with cetuximab in this study.

Randomization will be stratified by performance status (0-1 versus 2) and *EGFR* mutation type (exon 19 deletion versus L858R mutation). It is assumed that among patients with the exon 19 deletion, the median OS with afatinib alone will be 32 months based on the LUX-Lung 3 and 6 studies. It is also assumed that 56% of patients will have the exon 19 deletion. Further, it is assumed that among patients with the L858R mutation, the median OS with afatinib alone will be 21 months also based on the LUX-Lung studies. The median PFS for patients is assumed to be 13.7 months for patients with the exon 19 deletion and 10.8 months among patients with the L858R mutation among patients randomized to afatinib alone based on the LUX-Lung 3 study.

The addition of cetuximab will be judged to be superior if the true increase in median OS is 45% (hazard ratio = 0.69). A design with 90% power (not adjusting for Phase II analysis) and 0.025 1-sided type I error would require 304 deaths. Assuming exponential survival and uniform accrual, with 48 months of accrual and 14 months of follow-up, this design results in a sample size of 576 eligible *EGFR*-mutant NSCLC patients to detect a 45% improvement in median PFS using a 1-sided 0.025 level stratified log-rank test. Under these design parameters, an observed 25% or greater improvement in median OS (equivalent to an increase in median OS of 8 and 5.5 months for exon 19 and L858R patients will be considered evidence of benefit with the addition of cetuximab to afatinib. Assuming a 5% ineligibility rate, the total target accrual is 605.

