The primary objective for the new design is to compare PFS between the arms at the 1-sided 0.025 level. This analysis would take place when 134 PFS events or 70% of the events among eligible patients have been observed (whichever comes first and will depend on sample size attained). With 134 PFS events, this study has 90% power to detect a hazard ratio of 0.57 (75% improvement). The following table describes the analysis as a function of how many patients are accrued by the time of study closure:

Final Sample Size	# events at analysis	HR with 90% power	improvement in PFS
160	112	0.54	85%
180	126	0.56	78%
200	134	0.57	75%
212	134	0.57	75%

An interim analysis will take place when 64 PFS events have been observed. This analysis will be presented to the SWOG Data and Safety Monitoring Committee at the SWOG Group Meeting closest to this number of events. This analysis will evaluate if there is evidence to recommend early stopping of the study for futility by testing the null hypothesis at the 0.5 level, using a stratified log-rank test. If the p-value is 0.5 or greater, than the recommendation will be that there is insufficient evidence to continue accrual to this study.

Secondary Objectives under the revised design are to compare response rates, OS, time to treatment failure (TTF), time to treatment discontinuation (TTD), and toxicity.

Assuming 212 patients enrolled over 36 months with 14 months of additional follow-up, a one-sided log-rank test with an alpha of 0.025 has 90% power to detect an OS hazard ratio of 0.5, corresponding to a 2-fold increase in median OS, under the exponential distribution. Similarly, if it is assumed that the median TTF is 11 months, and the median TTD is also 11 months, there will be 92% power to detect a 70% increase in medians (hazard ratio of 0.59) for each of these endpoints.

Assuming 85% of patients will have measurable disease, 180 patients will be evaluable for the response comparison between arms. Response rates between the arms will be compared using a chi-squared test of independence at the 1-sided 5% level. With 90 patients per arm, this design has 93% power to detect at least a 22% difference in response rates between the arms and within each arm the rates can be estimated to within 10% with 95% confidence.

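### The revised plan should analyse by the two randomisation factors and name the final PFS test: a small, nearly free improvement, not a validity problem

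*Combined protocol and SAP*

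**What the plan says.** Section 6.0 randomises by dynamic balancing on performance status (0-1 against 2) and EGFR mutation type (exon 19 deletion against L858R). Section 5.2m admits performance status 2.

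The revised design (Section 11.2c, with its secondary-endpoint text repeated in 11.2d) treats the endpoints differently:

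- **Final PFS:** "The primary objective for the new design is to compare PFS between the arms at the 1-sided 0.025 level". No test, strata or hazard-ratio model is given.
- **64-event PFS interim:** futility is judged by "testing the null hypothesis at the 0.5 level, using a stratified log-rank test". The strata are not listed.
- **OS:** "a one-sided log-rank test with an alpha of 0.025 has 90% power to detect an OS hazard ratio of 0.5". This is a power statement, extended to two more endpoints by "Similarly, if it is assumed that the median TTF is 11 months, and the median TTD is also 11 months".
- **Response:** "Response rates between the arms will be compared using a chi-squared test of independence at the 1-sided 5% level". This is an explicit rule, and it is unstratified.

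The superseded sizing in Section 11.1 was based on a final comparison "using a 1-sided 0.025 level stratified log-rank test". Section 11.1 also gives mutation type different control medians: 32 and 21 months for OS, and 13.7 and 10.8 months for PFS (exon 19 deletion and L858R respectively). Section 18.1a says that the PFS difference seen in preliminary data was not significant.

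**The concern.** When allocation is balanced on prognostic factors, a test that ignores them is at most slightly conservative and gives up a little power. Both factors are already recorded for allocation, so using them needs no extra patients or events. How much is gained depends on how prognostic they are.

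The second issue is the primary endpoint. With no test named for final PFS, three readings remain open: unstratified, stratified by mutation type only (as Section 18.1a does for its T790M comparison), or stratified by both factors. Each is valid if fixed in advance. The primary analysis should not leave the choice to be made later.

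**Working it through.** **Inputs.** Section 11.2c: 134 PFS events at HR 0.57, 1-sided 0.025, 90% power; 212 patients over 36 months plus 14 months; OS HR 0.5; TTF/TTD median 11 months, HR 0.59, 92% power; response with 90 per arm, 22 points, 1-sided 5%, 93% power. Section 11.1: 56% exon 19 deletion and the medians above. Section 2.0: afatinib response rate 56%. Section 7.8: follow-up to 3 years. The share and outcome of performance status 2 patients, and response by mutation type, are not in the documents and are assumed below.

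**The plan's own figures.**

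- PFS (Schoenfeld): power = Φ(√d × |ln HR|/2 − 1.96). For d = 134, HR 0.57: 11.576 × 0.562/2 − 1.96 = 1.29, so 90.2%. The 126/0.56 and 112/0.54 rows give 90.2% and 90.3%.
- OS and TTF/TTD: the event probability is 1 − (e^(−14λ) − e^(−50λ))/(36λ), with λ = ln 2/median. OS gives about 94 deaths and 92.0% with the two stratum medians (stated 90%); a single median between 21 and 32 months gives 95% to 88%. TTF/TTD gives about 160 events and 91.5% (stated 92%).
- Response, 56% against 78%: (0.22 − 1.645 × 0.0701)/0.0682 = 1.54, so 93.8% (stated 93%).

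The stated figures are therefore consistent with ordinary formulas that do not use strata.

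**Time-to-event comparison.** 20,000 simulated trials per scenario: exponential times, 36-month uniform accrual, minimisation on both factors (biased coin 0.8, assumed), follow-up capped at 36 months, futility look not modelled. The stratified statistic is ΣU_k/√ΣV_k, where U_k and V_k are the log-rank score and variance in stratum k. Standard error is about 0.2 points for power and 0.1 for the paired difference.

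| Mutation strata only, no performance-status effect | Unstratified | Stratified |
|---|---|---|
| PFS, N=212, 134 events, HR 0.57 | 89.7% | 89.7% |
| PFS, N=180, 126 events, HR 0.56 | 89.6% | 89.8% |
| PFS, N=160, 112 events, HR 0.54 | 89.7% | 89.8% |
| OS, HR 0.5 | 89.5% | 90.0% |
| TTF/TTD, HR 0.59, single 11-month median | 90.7% | 90.5% |
| TTF/TTD, medians 12.2/9.6 (assumed) | 90.6% | 90.7% |

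The change is about −0.2 to +0.4 points, taken before rounding.

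| Assumed 15% with performance status 2 (unstratified / both factors) | Effect HR 1 | HR 2 | HR 3 |
|---|---|---|---|
| PFS, N=212 | 89.7 / 89.1% | 88.1 / 88.4% | 86.0 / 88.5% |
| OS | 89.8 / 89.7% | 90.7 / 91.4% | 90.2 / 92.3% |
| TTF/TTD (12.2/9.6) | 90.3 / 89.8% | 90.4 / 91.0% | 88.3 / 90.9% |

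Hazards are not rescaled across columns, so only the two figures in a cell should be compared. The change runs from about −0.6 to +2.7 points. Another run of the PFS case at HR 1 gave 90.0 / 89.2%, a loss of 0.8. Under no treatment effect, PFS rejection is 2.3-2.6% unstratified and 2.5-2.6% stratified. On the mutation strata, the two PFS verdicts differ in 1.5% of trials at HR 0.57 and in 0.6% under no effect.

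**Response comparison.** 200,000 simulations, 90 per arm split 50/40 by mutation type, 22-point gain. The CMH statistic is Σ(a_k − n_1k m_k/n_k) divided by the square root of Σ n_1k n_0k m_k (n_k − m_k)/(n_k²(n_k − 1)), where a_k is responders on the combination, m_k all responders, and n_1k, n_0k and n_k the arm sizes and total in stratum k.

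| Control response, exon 19 / L858R | Chi-squared | CMH |
|---|---|---|
| 56% / 56% | 93.7% | 93.7% |
| 61% / 50% (assumed) | 93.8% | 94.0% |
| 65% / 45% (assumed) | 94.2% | 94.7% |
| 75% / 35% (assumed) | 96.0% | 97.6% |

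Size is 5.3% (chi-squared) and 5.1% (CMH) at 56%/56%, and 3.9% and 4.9% at 75%/35%. With strata on both factors (61%/50%, 15% performance status 2, response 30 points lower in that group, all assumed), power is 93.5% and 93.8%, and size 4.3% and 5.3%.

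**The case against.** The case for leaving the text alone is strong on size. On the plan's own inputs the gain is near zero, and for PFS its direction is not established: a smaller set of 4,000 runs with exact balance within strata gave 88.9% stratified against 89.4% unstratified, within simulation noise. The visible gains need a strong performance-status effect or very unequal response rates, none of it documented. An unstratified chi-squared test is an acceptable prespecified choice for a secondary endpoint. All of this stands, and it is why the point is minor.

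A reader might infer that the revision dropped stratification for OS, TTF and TTD. The documents do not support that. Those sentences are power statements, and Section 11.2b describes the original final analysis as a plain 1-sided log-rank test although Section 11.1 had sized it as stratified. The bare phrase may be shorthand, so stratification is unspecified rather than excluded.

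A reader might also infer that final PFS is meant to be unstratified. The introduction to 11.2c lists changes to endpoint, sample size and accrual, not to the test, and the interim on the same endpoint is stratified. Carry-over is the natural reading, but it is not written.

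Timing is a fair objection too. The document is stamped closed on 04/23/2018, while the afatinib adverse-event list in Section 3.1 is dated June 15, 2020. Between-arm results may already have been seen, so a fallback is needed for every endpoint.

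**Conclusion.** Minor, and worth doing because it is cheap. The definite facts are that response has an unstratified rule, final PFS has no named test, and the OS, TTF and TTD sentences do not mention strata. On the documented mutation strata the effect on power is about −0.2 to +0.4 points for PFS, OS and TTF/TTD, and zero for response at 56% in both strata. Gains of up to about 2.7 points (time to event) and 1.6 points (response) rest on assumed prognostic differences. The loss from stratifying by an uninformative performance status is up to about 0.8 points.

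Two stronger readings do not hold. This is not a false-positive problem: the unstratified PFS test rejects at 2.3-2.6% against a nominal 2.5%. Nor is meaningful power being lost on the plan's own figures, so stratification should not be presented as recovering a shortfall. The most useful part of the change is the missing line for the primary test.

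**What to change.** In Sections 11.2c and 11.2d, state that:

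- final PFS (1-sided 0.025), OS, TTF and TTD use a log-rank test stratified by the two Section 6.0 factors, with a Cox hazard ratio stratified the same way;
- response uses a 1-sided 5% CMH test on the same strata.

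Fix the strata now rather than leaving them to a later choice. Little depends on this even if performance status 2 is rare: with an assumed 5% (0.05 × 212, about 11 patients), PFS power by mutation type alone against both factors is 89.2% against 88.7% if performance status has no effect, and 88.8% against 88.7% at HR 2.

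Date the change before between-arm results are seen outside the monitoring committee. If any such result has been seen, keep chi-squared as the primary response test with CMH beside it. For PFS, OS, TTF and TTD, report both stratified and unstratified results, and label any test chosen after results were seen as not prespecified.

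Leave the toxicity tests as written; the documents link neither factor to toxicity. The cost is wording plus the small possible power loss given above. Sample size, event count and alpha do not change.

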11.3 Accrual

The estimated accrual rate is 5-6 patients per month with an assumed 5% ineligibility rate, which will provide the total goal of 223 patients over a 36 month period. However, there will be a hard stop on accrual on October 1, 2018, even if the accrual goal of 212 eligible patients has not been met. In addition, if the study has not accrued 173 patients by April 14, 2018 (the SWOG Spring 2019 meeting), then the study will be closed to further accrual.

11.4 Data and Safety Monitoring

A Data and Safety Monitoring Committee will oversee the conduct of the study. The Committee consists of four members from outside of the SWOG, 3 SWOG members, 3 non-voting representatives from the National Cancer Institute (NCI), and the Group Statistician (non-voting). The members of this Committee will receive confidential reports

every 6 months from the SWOG Statistics and Data Management Center, and will meet at the Group's bi-annual meetings as necessary. The Committee will be responsible for decisions regarding possible termination and/or early reporting of the study.

12.0 DISCIPLINE REVIEW

This section does not apply to this protocol.

13.0 REGISTRATION GUIDELINES

13.1 Registration Timing

Patients must be registered prior to initiation of treatment (no more than 14 calendar days prior to planned start of treatment).

13.2 Investigator/Site Registration

Prior to the recruitment of a patient for this study, investigators must be registered members of a Cooperative Group. Each investigator must have an NCI investigator number and must maintain an "active" investigator registration status through the annual submission of a complete investigator registration packet to CTEP.

a. CTEP Registration Procedures

Food and Drug Administration (FDA) regulations and National Cancer Institute (NCI) policy require all individuals contributing to NCI-sponsored clinical trials to register and to renew their registration annually. To register, all individuals must obtain a Cancer Therapy Evaluation Program (CTEP) Identity and Access Management (IAM) account (<https://ctepcore.nci.nih.gov/iam>). In addition, persons with a registration type of Investigator (IVR), Non-Physician Investigator (NPIVR), or Associate Plus (AP) (i.e., clinical site staff requiring write access to OPEN, RAVE, or TRIAD or acting as a primary site contact) must complete their annual registration using CTEP's web-based Registration and Credential Repository (RCR) (<https://ctepcore.nci.nih.gov/rcr>). Documentation requirements per registration type are outlined in the table below.

Documentation Required	IVR	NPIVR	AP	A
FDA Form 1572	✓	✓		
Financial Disclosure Form	✓	✓	✓	
NCI Biosketch (education, training, employment, license, and certification)	✓	✓	✓	
HSP/GCP training	✓	✓	✓	
Agent Shipment Form (if applicable)	✓			
CV (optional)	✓	✓	✓	

An active CTEP-IAM user account and appropriate RCR registration is required to access all CTEP and CTSU (Cancer Trials Support Unit) websites and applications. In addition, IVRs and NPIVRs must list all clinical practice sites and IRBs covering their practice sites on the FDA Form 1572 in RCR to allow the following:

- Added to a site roster
- Assigned the treating, credit, consenting, or drug shipment (IVR only) tasks in OPEN
- Act as the site-protocol PI on the IRB approval
- Assigned the Clinical Investigator (CI) role on the Delegation of Tasks Log (DTL).

Additional information can be found on the CTEP website at <https://ctep.cancer.gov/investigatorResources/default.htm>. For questions, please contact the RCR **Help Desk** by email at [contact].

b. CTSU Registration Procedures

This study is supported by the NCI Cancer Trials Support Unit (CTSU).

1. **IRB Approval:**

Each investigator or group of investigators at a clinical site must obtain IRB approval for this protocol and submit IRB approval and supporting documentation to the CTSU Regulatory Office before they can be approved to enroll patients. Assignment of site registration status in the CTSU Regulatory Support System (RSS) uses extensive data to make a determination of whether a site has fulfilled all regulatory criteria including but not limited to: the following:

- An active Federal Wide Assurance (FWA) number
- An active roster affiliation with the Lead Network or a participating organization
- A valid IRB approval
- Compliance with all protocol specific requirements.

In addition, the site-protocol Principal Investigator (PI) must meet the following criteria:

- Active registration status
- The IRB number of the site IRB of record listed on their Form FDA 1572
- An active status on a participating roster at the registering site.

Sites participating on the NCI CIRB initiative that are approved by the CIRB for this study are not required to submit IRB approval documentation to the CTSU Regulatory Office. For sites using the CIRB, IRB approval information is received from the CIRB and applied to the RSS in an automated process. Signatory Institutions must submit a Study Specific Worksheet for Local Context (SSW) to the CIRB via IRB Manager to indicate their intent to open the study locally. The CIRB's approval of the SSW is then communicated to the CTSU Regulatory Office. In order for the SSW approval to be processed, the Signatory Institution must inform the CTSU which CIRB-approved institutions aligned with the Signatory Institution are participating in the study.

2. **Downloading Site Registration Documents:**

Site registration forms may be downloaded from the **S1403** protocol page located on the CTSU members' website.

- Go to <https://www.ctsu.org> and log in to the members' area using your CTEP-IAM username and password
- Click on the Protocols tab in the upper left of your screen
- Either enter the protocol # in the search field at the top of the protocol tree, or
- Click on the By Lead Organization folder to expand
- Click on the SWOG link to expand, then select trial protocol **S1403**.
- Click on LPO Documents, select the Site Registration documents link, and download and complete the forms provided.

3. **Requirements For S1403 Site Registration:**

- CTSU Transmittal Sheet (optional)
- IRB approval (For sites not participating via the NCI CIRB; local IRB documentation, an IRB-signed CTSU IRB Certification Form, Protocol of Human Subjects Assurance Identification/IRB Certification/Declaration of Exemption Form, or combination is accepted)

4. **Submitting Regulatory Documents:**

Submit required forms and documents to the CTSU Regulatory Office via the Regulatory Submission Portal, where they will be entered and tracked in the CTSU RSS.

Regulatory Submission Portal: www.ctsu.org (members' area) → Regulatory Tab → Regulatory Submission

When applicable, original documents should be mailed to:

CTSU Regulatory Office
[name]
[name]

Institutions with patients waiting that are unable to use the Portal should alert the CTSU Regulatory Office immediately at [contact] in order to receive further instruction and support.

5. **Checking Your Site's Registration Status:**

You can verify your site registration status on the members' section of the CTSU website.

- Go to <https://www.ctsu.org> and log in to the members' area using your CTEP-IAM username and password
- Click on the Regulatory tab at the top of your screen
- Click on the Site Registration tab
- Enter your 5-character CTEP Institution Code and click on Go

Note: The status given only reflects compliance with IRB documentation and institutional compliance with protocol-specific requirements as outlined by the Lead Network. It does not reflect compliance with

protocol requirements for individuals participating on the protocol or the enrolling investigator's status with the NCI or their affiliated networks.

13.3 OPEN Registration Requirements

The individual registering the patient must have completed the appropriate SWOG Registration Worksheet. The completed form must be referred to during the registration but should not be submitted as part of the patient data.

Patient enrollment will be facilitated using the Oncology Patient Enrollment Network (OPEN). OPEN is a web-based registration system available on a 24/7 basis. To access OPEN, the site user must have an active CTEP-IAM account (check at <https://ctepcore.nci.nih.gov/iam>) and a 'Registrar' role on either the LPO or participating organization roster. Registrars must hold a minimum of an AP registration type. If a DTL is required for the study, the registrar(s) must also be assigned the OPEN Registrar task on the DTL.

All site staff will use OPEN to enroll patients to this study. It is integrated with the CTSU Enterprise System for regulatory and roster data and, upon enrollment, initializes the patient in the Rave database. OPEN can be accessed at <https://open.ctsu.org> or from the OPEN tab on the CTSU members' side of the website at <https://www.ctsu.org>. To assign an IVR or NPIVR as the treating, crediting, consenting, drug shipment (IVR only), or investigator receiving a transfer in OPEN, the IVR or NPIVR must list on their Form FDA 1572 in RCR the IRB number used on the site's IRB approval. If a DTL is required for the study, the IVR or NPIVR must also be assigned the appropriate OPEN-related tasks on the DTL.

OPEN will also ask additional questions that are not present on the SWOG Registration Worksheet. The individual registering the patient must be prepared to provide answers to the following questions:

- a. Institution CTEP ID
- b. Protocol Number
- c. Registration Step
- d. Treating Investigator
- e. Credit Investigator
- f. Patient Initials
- g. Patient's Date of Birth
- h. Patient SSN (SSN is desired, but optional. Do not enter invalid numbers.)
- i. Country of Residence
- j. ZIP Code
- k. Gender (select one):
 - Female Gender
 - Male Gender
- l. Ethnicity (select one):
 - Hispanic or Latino

- Not Hispanic or Latino
- Unknown

m. Method of Payment (select one):

- Private Insurance
- Medicare
- Medicare and Private Insurance
- Medicaid
- Medicaid and Medicare
- Military or Veterans Sponsored NOS
- Military Sponsored (Including Champus & Tricare)
- Veterans Sponsored
- Self Pay (No Insurance)
- No Means of Payment (No Insurance)
- Other
- Unknown

n. Race (select all that apply):

- American Indian or Alaska Native
- Asian
- Black or African American
- Native Hawaiian or other Pacific Islander
- White
- Unknown

